For families randomised to receive MBT-PP, Tavistock Relationship (TR) will contact the family on receipt of the allocation from the GL to arrange initial sessions with each parent. Contact will be made by telephone, and preferences for Zoom/Teams to attend MBT-PP will be discussed.

It should be noted that MBT-PP commences with a clinical assessment, which can occasionally result in the decision that the intervention is not suitable for a particular family, due to risk management (i.e. concerns that the therapeutic process may exacerbate problems, or disclosures of abuse). In such cases, the family will be deemed ineligible and will be referred onwards to other services as appropriate. However, for the purposes of the Intention-to-Treat (ITT) analyses, these families will be included according to their original allocation.

Sample size calculations

Internal pilots enable data from the ‘pilot’ and ‘efficacy’ stages to be combined in order to increase sample size (and hence statistical sensitivity). Internal pilots are best thought of as a smaller scale efficacy trial which might be undertaken to gain some evidence of promise before funding a larger scale efficacy trial. All types of pilot could provide ‘evidence of promise’ and also are useful for obtaining empirical estimates to help improve the precision / accuracy of power analyses for an efficacy trial. What makes ‘internal pilots’ distinct is the pre-specified plan to combine data from the ‘pilot’ and ‘efficacy’ stages. This results in greater restrictions on adaptations between these stages; most strongly around the intervention (e.g., how it is implemented and theorised) but also around evaluation design (primary outcome, trial design). Programmes that are well developed and have some exposure to type-3 evaluation methodologies (QED if not RCT) might be suitable for this. For programmes that may evolve between the two stages, combining the two sets of data will be less reliable. In summary, whilst ‘internal pilots’ can bring additional methodological benefits compared with standard (‘external’) pilots, this does come at a cost of reduced flexibility in adaptation.

Based on the previous small-scale randomised study of MBT-PP (Hertzmann et al., 2016), this trial design assumes that an internal pilot is suitable and effect sizes for both pilot and efficacy stages will be reported alongside the combined effect size in the final evaluation findings.

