We recommend a total sample size (pilot + efficacy) of 350 families to best ensure that the CRT design achieves an MDES of 0.22 SDs. In the event of zero attrition, a sample of 350 families (700 CYP) has MDES estimates between 0.15 and 0.20 SDs (depending on ICC and covariate explanatory power). With the assumption of 10% attrition, the randomised ITT sample of 350 would lead to a final sample of 315 families (630 CYP). Indicative MDES estimates for a sample of 315 families are between 0.16 and 0.21 SDs. Even in the event of attrition being 20%, the final sample (of 280 families, 560 CYP) results in indicative MDES estimates between 0.17 and 0.22 SDs. These indicative MDES estimates include an assumption that attrition will be random; which is why they are labelled as ‘indicative’. A missing data analysis will be undertaken to examine this assumption and, if appropriate, multiple imputation will be used to estimate missing values (within follow-on sensitivity analyses).

To combine the pilot and efficacy stage samples, the intervention needs to be as consistent as possible in both stages – although effect sizes for the two separate pilot and efficacy stages

will be reported alongside the combined effect size. Consistency in effect sizes along with the underlying Theory of Change would result in robust findings for the combined sample.

In addition to providing data to improve statistical sensitivity for the efficacy trial, the internal pilot would also be able to provide empirical estimates for both ICC and covariate explanatory power. This would allow the power analyses to be updated with empirical estimates (e.g., in the Statistical Analysis Plan).

In the pilot phase of the project we expect to reach and randomise 140 families (280 CYP). In the efficacy phase of the project, we expect to reach and randomise 210 families (420 CYP), making a total of 700 CYP over the entire recruitment phase (pilot + efficacy combined).

Table 4 has been completed assuming a total (pilot+efficacy) sample of 350 families (700 CYP). Please see above for details behind making this assumption. The estimations for pre-test/post-test correlations (family and CYP levels) and the ICC value (just family) cover a range of values. Data from the internal pilot will be used to update these with empirical estimates.

Table 4. Sample size calculations

		PARAMETER
Minimum Detectable Effect Size (MDES)		0.15 – 0.20, depending on ICC and covariate explanatory power

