Pre-test/ post-test correlations	level 1 (participant)	0.50 to 0.70 (R^2 between 0.25 & 0.49)
	level 2 (cluster)	0.50 to 0.70 (R^2 between 0.25 & 0.49)
Intracluster correlations (ICCs)	level 1 (participant)	Not appropriate in this case. There will be residual variance but ICCs relate to clusters not individuals. The proportion of residual variance is assumed to be between 0.85 and 0.99
	level 2 (cluster)	0.01 to 0.15
Alpha ⁷		0.05
Power		0.80
One-sided or two-sided?		Two
Average cluster size (if clustered)		2 CYP per family
Number of clusters ⁸	Intervention	175
	Control	175

	Total	350
Number of participants	Intervention	350
	Control	350
	Total	700

With an attrition rate of 10%, and assuming that attrition was random, the indicative MDES estimates would be between 0.16 and 0.21 sds.

Internal Pilot Study

Internal pilots enable data from the ‘pilot’ and ‘efficacy’ stages to be combined in order to increase sample size (and hence statistical sensitivity). Internal pilots are best thought of as a smaller scale efficacy trial which might be undertaken to gain some evidence of promise before committing funding a larger scale efficacy trial. All types of pilot could provide ‘evidence of promise’ and also are useful for obtaining empirical estimates to help improve the precision / accuracy of power analyses for an efficacy trial. What makes ‘internal pilots’ distinct is the pre-specified plan to combine data from the ‘pilot’ and ‘efficacy’ stages. This results in greater restrictions on adaptations between these stages; most strongly around the intervention (e.g., how it is implemented and theorised) but also around evaluation design (primary outcome, trial design). Programmes that are well developed and have some exposure to type-3 evaluation methodologies (QED or RCT) are considered suitable for this. MBT-PP meets the criteria of being well established, and evidence of promise was found in a small-scale, underpowered RCT (e.g., Hertzmann et al., 2016; 2017). Our design assumes that an internal pilot is suitable and effect sizes for both pilot and efficacy stages will be reported alongside the combined effect size in the final evaluation findings (should the pilot continue to efficacy stage).

The aims of the internal pilot study will be to assess:

- a) The extent to which the referral pathways are working, i.e., whether sufficient referrals are flowing into the project, and whether these referrals are meeting eligibility requirements

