March 2023-April 2024	
Pilot baseline data collection.
 
Referrals that come in from March-Dec will have post-intervention data included in the pilot study primary outcome analysis. Referrals coming in Jan-April will have baseline data only included in the analyses to address the aims of the pilot study regarding recruitment and acceptability.
	AM & EC, with input from rest of Evaluation Team

May-June 2024
	
Transition.
 
Evaluators prepare draft report on pilot, for submission end of May. YEF make progression decision by late June.
	
SD, JR, with input from rest of Evaluation Team.
 
AM & EC, with input from rest of Evaluation Team

July 2024-Dec 2024
	
Reflect on feedback from report. Make any alterations necessary to procedures.
 
Efficacy baseline data collection.
 
IPE data collection.
	
AM & EC, with input from rest of Evaluation Team

Jan-April 2025
	
Efficacy post-intervention data collection
 
IPE data collection.
	
AM & EC, with input from rest of Evaluation Team

May-Dec 2025
	
Complete 3 month follow up data collection.
 
Complete IPE data collection.
 
Analysis and reporting.
	
AM & EC, with input from rest of Evaluation Team.
 
SD, JR, with input from rest of Evaluation Team.

References

- Adamsons, K., & Pasley, K. (2006). Coparenting following divorce and relationship dissolution. In M. Fine & J. Harvey (Eds.), *Handbook of Divorce and Relationship Dissolution*, pp. 241-262. Mahwah, NJ: Lawrence Erlbaum
- Altman, D.G. & Bland, M.J. (2005) Statistics Notes: Treatment allocation by minimisation. *BMJ* 330 p843
- Arnold, D. S., O'leary, S. G., Wolff, L. S., & Acker, M. M. (1993). The Parenting Scale: a measure of dysfunctional parenting in discipline situations. *Psychological Assessment*, 5(2), 137. <https://doi.org/10.1037/1040-3590.5.2.137>

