To examine evidence of differential impact for Tavistock MBT, three subgroup analyses are planned for the (mothers SDQ-TD) primary outcome. Differential impact will be examined relating to CYP age and ethnicity and the relationship status of the parents. All analyses of subgroups are exploratory.

Two analysis stages will be used to examine evidence of differential impact. Stage one will add two terms to the ITT analysis model. A main effects term will be added along with a term that interacts with group membership. If the interaction term is observed to be statistically significant ($p < 0.05$, two tailed), this provides evidence of differential impact and so separate impact analyses will be undertaken for different CYP subsamples.

For example, to examine evidence of differential impact for different aged CYP, CYP age will be included as a main effect (CYP_Age_{ij}) and as an interaction with the family-level group identifier ($T_j \times CYP_Age_{ij}$), as described in equation 4.0

$$[4.0] Y_{ij} = \beta_0 + \beta_1 T_j + \beta_2 (X_{ij} - \bar{X}_j) + \beta_3 (\bar{X}_j - \bar{X}) + \beta_4 CYP_Age_{ij} + \beta_5 T_j \times CYP_Age_{ij} + \beta_{6..9} [MIN DUM]_j + \vartheta_j + \varepsilon_{ij}$$

If the β_5 interaction coefficient is observed to be statistically significant, a second stage analysis will estimate impact for two subsamples; CYP aged 7-11 and CYP aged 12-14³. This

³ These age groupings were selected to reflect the Primary (Key Stage 2) and Secondary (Key Stage 3) educational phases and used as controls in the minimisation.

will be done by running separate analyses (described in equation 2.0 above) for these two CYP age groups.

To examine evidence of differential impact relating to the relationship status of parents, a relationship status binary family-level main effect(s) term (*e.g.* $FAM_RELSTATUS_{ij}$) would be added along with interaction with the family-level group identifier ($T_j * FAM_RELSTATUS_{ij}$ etc). $FAM_RELSTATUS_{ij}$ takes the value of 0 (intact) or 1 (separated). If the interaction term is observed to be statistically significant, a second stage analysis will estimate impact separately for CYP from intact and from separated families.

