To examine evidence of a different impact at pilot and stage 2 of the evaluation we will first statistically summarise the mothers SDQ TD scores at T2 for the two stages alongside the scores for the combined ‘efficacy with internal pilot’ sample. These analyses will be substantively informed by the IPE and evidence of any changes in the theory, delivery, fidelity and compliance of MBT between pilot and stage 2. Following the descriptive statistical summary, we will adopt an similar approach to the relationship status subsample analysis specified above by including two additional variables to the ITT hierarchical linear model. A binary family-level ‘Stage’ main effect(s) term (*e.g.* $FAM_TrialStage_{ij}$) would be added along with interaction with the family-level group identifier ($T_j * FAM_TrialStage_{ij}$ etc). $FAM_TrialStage_{ij}$ will take the value of 0 (pilot) or 1 (stage 2). If the interaction term is observed to be statistically significant, a follow-on analysis will estimate impact separately for CYP in the pilot and stage 2 evaluations. This will be compared with the ITT estimate for the combined ‘efficacy trial with internal pilot’ evaluation and be discussed with reference to IPE findings on changes to the theory, implementation, fidelity and compliance for the MBT-PP programme between the two stages. This is illustrated in Table 8 below:

Table 8. Sensitivity Analysis: mothers SDQ-TD primary outcome at pilot and stage 2

Analysis and Sample	Level 1 (CYP) Covariates	Level 2 (Family) Covariates	Outcome Variable
Main Effects Final Impact Model (Complete ITT Sample)	Mothers SDQ-TD score at T1/baseline (Centred around family mean)	Mean mothers SDQ-TD score at T1/baseline (Centred around grand mean) Group membership (MBT or TAU) Four Minimisation Variables: CYP ages (2), parental ethnicity (1), relationship status (1);	CYP level mothers SDQ-TD (raw) score at T2 (16 weeks following minimisation)

Interaction Model (Complete ITT Sample)	Mothers SDQ-TD score at T1/baseline (Centred around family mean)	Mean mothers SDQ-TD score at T1/baseline (Centred around grand mean) Group membership (MBT or TAU) Four Minimisation Variables: CYP ages (2), parental ethnicity (1), relationship status (1) TrialStage (0=pilot, 1=stage 2) Interaction: Group Membership*TrialStage	CYP level mothers SDQ-TD (raw) score at T2 (16 weeks following minimisation)
---	--	---	--

Assuming a statistically significant interaction term...

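### The SAP makes the separate pilot and stage 2 effect sizes depend on a low-powered interaction test, although the protocol commits to reporting both without that condition

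*SAP*

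**What the plan says.** **Protocol.** The opening part of Sample size calculations says that "effect sizes for both pilot and efficacy stages will be reported alongside the combined effect size in the final evaluation findings". The Assumptions subsection repeats the commitment for "effect sizes for the two separate pilot and efficacy stages" and adds that consistent effect sizes, together with the Theory of Change, would make the combined findings robust. Internal Pilot Study makes the commitment a third time, with one qualifier: "combined effect size in the final evaluation findings (should the pilot continue to efficacy stage"). None of the three statements mentions a significance test.

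**SAP.** Under Further analyses, the comparison of stages begins with a description: "we will first statistically summarise the mothers SDQ TD scores at T2 for the two stages". A trial-stage term and its interaction with arm are then added to the primary model in the complete ITT sample. Stage-specific impact comes last and is conditional: "If the interaction term is observed to be statistically significant, a follow-on analysis will estimate impact separately" for the pilot and stage 2. Table 8 has the same structure, placing the stage-specific null and impact models below a line that assumes a significant interaction. The significance level is not restated there. The procedure is said to resemble the relationship-status subgroup analysis, and Subgroup analyses sets 0.05, two-tailed. The SAP gives no power for this interaction and does not explain the departure from the protocol.

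**The concern.** The two documents differ on whether a promised result is shown. The protocol presents the stage effect sizes as part of the support for the combined result, so a reader of the final report should be able to see them. Under the SAP, the split-sample estimates appear only if an interaction test succeeds, in a trial sized for the main effect alone.

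Two consequences follow if that test has low power. First, the stage effect sizes will usually not be produced as reported results, even when the stages differ by an amount comparable to the whole target effect. Second, when they are produced, they have passed a significance filter, so a modest true difference will tend to look larger than it is. Stage matters in this trial because the SAP itself foresees possible changes in theory, delivery, fidelity and compliance between the pilot and stage 2.

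**Working it through.** **Inputs** (SAP, Sample size calculations): 1.4 CYP per family; ICC 0.27; R² 0.61 (family) and 0.75 (CYP); allocation 0.50; m = 6; two-sided alpha 0.05; power 0.80; 250 families in total; 90 families at pilot. The 160 stage 2 families are inferred as 250 − 90; the SAP does not state this figure.

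**Step 1: reproduce the SAP's figures (equation 1.0).**

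The variance term is 0.27 × (1 − 0.61) + 0.73 × (1 − 0.75)/1.4 = 0.1053 + 0.1304 = 0.2357. With equal allocation, SE = 2 × √(0.2357/J), and MDES = (t.975 + t.80) × SE on J − m − 2 degrees of freedom.

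- J = 250: SE 0.0614, multiplier 2.813, MDES 0.173 (SAP: 0.17).
- J = 90: SE 0.1023, multiplier 2.835, MDES 0.290 (SAP: 0.29).

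**Step 2: stage-specific precision.**

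- Pilot, 90 families: SE 0.102 SD, so the 95% CI is about ±1.96 × 0.102 = ±0.20 SD.
- Stage 2, 160 families: SE 0.077 SD, so the 95% CI is about ±1.96 × 0.077 = ±0.15 SD.

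**Step 3: the interaction.**

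SE = √(0.1023² + 0.0768²) = 0.128 SD. With m = 8 (stage and interaction added), there are 250 − 8 − 2 = 240 degrees of freedom and the multiplier is 2.813, so MDES = 2.813 × 0.128 = 0.36 SD. Significance needs an observed difference of at least 1.970 × 0.128 = 0.25 SD. Power comes from the noncentral t distribution.

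| Families (pilot v stage 2) | Interaction SE | MDES | Power at 0.10 | at 0.17 | at 0.20 SD |
|---|---|---|---|---|---|
| 90 v 160 | 0.128 | 0.36 | 12% | 26% | 34% |
| 125 v 125 | 0.123 | 0.35 | 13% | 28% | 37% |
| 72 v 128 (20% attrition) | 0.143 | 0.40 | 11% | 22% | 29% |
| 140 v 210 (protocol's split, SAP parameters) | 0.106 | 0.30 | 16% | 36% | 47% |

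If R² at both levels were 0.49 or 0.25, the ends of the protocol's range, the 90 v 160 MDES would be 0.47 or 0.57 SD.

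**Step 4: what the condition does.**

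For 90 v 160, the stage models are not triggered with probability 1 − 0.34 = 66% at a true difference of 0.20 SD, 74% at 0.17 and 88% at 0.10. With no true difference the figure is 95%. Power reaches 50% only at about 0.25 SD. A true difference of 0.17 SD passes the filter only when it is estimated at 0.25 SD or more, which is about 1.5 times its size (0.25/0.17).

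**The case against.** The strongest reply is that little is lost. The interaction model is fitted whatever its p-value. With pilot coded 0 and stage 2 coded 1, the arm coefficient is the adjusted pilot effect, and that coefficient plus the interaction is the adjusted stage 2 effect. Only the split-sample refits are conditional. Scores by stage are summarised regardless, and Further analyses opens by stating, without condition, the aim of examining impact at both stages. The protocol's Timeline also says that referrals from March to December "will have post-intervention data included in the pilot study primary outcome analysis", so a pilot estimate may exist elsewhere. Requiring a significant interaction before splitting the sample is an ordinary guard against over-reading noise, and the SAP uses it for its exploratory subgroups.

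Much of this stands. A reader might infer that the stage effects will never be reported. The documents do not support that, for the reasons just given. A reader might also infer that a non-significant test will be taken as proof of consistency, but the SAP does not say how such a result will be interpreted. Nor does conditional reporting remove all the evidence on pooling. The protocol also relies on consistency of the intervention, and the SAP brings in process-evaluation findings.

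What remains is that none of these routes meets the commitment. The SAP does not undertake to report the two effects contained in the interaction model. The T2 summary is of scores, not adjusted impact. A pilot analysis on part of the pilot referrals supplies neither a full pilot effect nor a stage 2 effect. The subgroup guard suits analyses labelled exploratory, whereas the stage effects were promised.

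**Conclusion.** The discrepancy is explicit and unexplained. The protocol commits to both stage effect sizes subject only to progression past the pilot; the SAP makes the separate estimates subject to a significant interaction. The SAP as written will probably not trigger them for any true stage difference up to 0.20 SD, the overall effect the trial is sized to detect, because power at 0.20 SD is between 29% and 47% across the splits tabulated.

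The size rests on three assumptions: the SAP's pilot-based ICC and R² values; a stage split that the SAP does not state; and a true stage difference that is unknown and so shown as a range. Low power does not depend on the particular split, and weaker covariates would lower it further. Overstatement after the filter is a tendency when the true difference is small relative to about 0.25 SD; it need not occur for a large one.

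A reader might also infer that the pilot treatment effect influenced the cut from 350 to 250 families. The SAP describes using pilot outcomes from 43 families for the ICC and explanatory power, and does not say that the treatment effect was used.

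This is a reporting fault in a sensitivity analysis. The primary ITT estimate, its test and the sample size are unaffected. It should be corrected because it concerns a commitment the protocol makes three times.

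**What to change.** In the SAP's Further analyses and in Table 8, remove the significance condition for trial stage. State that the pilot, stage 2 and combined effect sizes will be reported with 95% confidence intervals whatever the interaction p-value, beside the stage-by-arm interaction estimate and its 95% confidence interval. State also that interpretation of any stage difference will be led by the interaction estimate and its interval, not by comparing the two stage results by eye.

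The cost is a change of wording and two impact models that Table 8 already lays out, with their null models, on data already due to be collected. There is a small downside: readers may over-read a chance difference between two imprecise estimates (about ±0.20 SD for the pilot and ±0.15 SD for stage 2). Leading with the interaction interval is meant to limit that.
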